When assessing ENDS use, significant inter-subject variability has been described for human puffing topography (HPT) parameters, especially puff duration, puff frequency, and flow rate [6]. Experienced e-cigarette users may extract more nicotine by puffing with a low flow rate and long duration puffs in comparison to cigarette smokers. E-cigarette design features also affect nicotine exposure; increasing the battery voltage output and e-liquid nicotine concentration increases the nicotine delivery [7]. Differences in puffing behavior (such as puff duration or depth of inhalation) resulted in a faster absorption rate and a higher amount of nicotine absorption in experienced e-cigarette users as compared to naïve e-cigarette users when using the same e-cigarette [8]. Battery output, type of wicks, ventilation holes, and other mechanical characteristics of each individual e-cigarette product determine how much aerosol and nicotine is released. More effective and appealing e-cigarette products to provide satisfying alternatives to smoking has led to e-liquids containing 'nicotine salts'. Nicotine salts are formed by the reaction of nicotine with a suitable acid and are less volatile than freebase nicotine [9]. As a result, a greater fraction of the nicotine in the salt form is expected to remain in inhaled aerosol droplets until the aerosol reaches the alveoli for pulmonary absorption.

Confidentiality Statement

Data and information contained in this document are considered to constitute trade secrets and confidential commercial information, and the legal protections provided to such trade secrets and confidential information are hereby claimed under the provisions of applicable law. No part of this document may be publicly disclosed without the written consent of Philip Morris Products S.A.

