3.3 Exploratory Objectives and Endpoints

1. To describe the associations between P4M3 Gen 2.0 HPT parameters, PD and PK endpoints.

Related Endpoints (Day 1 to Day 3)

- Product liking by the VAS-liking assessment and C_{max}, T_{max}, and AUC_{0-infinity} PK endpoints
- Product liking by the VAS-liking assessment and per-product use experience parameters from the MDEDR puffing topography device for 2 variants of P4M3 Gen 2.0

Confidentiality Statement

Data and information contained in this document are considered to constitute trade secrets and confidential commercial information, and the legal protections provided to such trade secrets and confidential information are hereby claimed under the provisions of applicable law. No part of this document may be publicly disclosed without the written consent of Philip Morris Products S.A.

Additional Study Assessments (for eligibility assessment and baseline characteristics):

- Serology for human immunodeficiency virus (HIV) 1/2 and hepatitis B and C
- Pregnancy test (all females)
- Urine cotinine test
- Urine drug test including testing for amphetamine type substances, barbiturates, benzodiazepines, cannabinoids, cocaine, opiates
- Alcohol breath test
- Nicotine dependence assessed by Fagerström Test for Nicotine Dependence
- Cytochrome P450 2A6 (CYP2A6) activity expressed as trans-3'-hydroxycotinine / cotinine molar metabolite ratio in plasma

Confidentiality Statement

Data and information contained in this document are considered to constitute trade secrets and confidential commercial information, and the legal protections provided to such trade secrets and confidential information are hereby claimed under the provisions of applicable law. No part of this document may be publicly disclosed without the written consent of Philip Morris Products S.A.

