12.7 Exploratory Analyses

Exploratory analyses endpoints are listed in section [3.3](#).

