12.7.2 Inferential Analysis

An analysis of covariance (ANCOVA) will be conducted by product use. The PK parameters will be transformed in the natural logarithmic scale. The model will include terms for sequence, period and product liking by the VAS-liking assessment. The results of this analysis will be presented by product in terms of:

- The percentage of variance explained by product liking by the VAS-liking assessment

Confidentiality Statement

Data and information contained in this document are considered to constitute trade secrets and confidential commercial information, and the legal protections provided to such trade secrets and confidential information are hereby claimed under the provisions of applicable law. No part of this document may be publicly disclosed without the written consent of Philip Morris Products S.A.

- The standardized effect of product liking by the VAS-liking assessment on the endpoint, defined as the mean effect divided by the square root of its variance.

Another analysis of covariance (ANCOVA) will be conducted similarly at the exception that it will be performed overall using mixed effects ANCOVA where the model will include additionally the subject as a categorical random effect to model the within subject correlations.

Confidentiality Statement

Data and information contained in this document are considered to constitute trade secrets and confidential commercial information, and the legal protections provided to such trade secrets and confidential information are hereby claimed under the provisions of applicable law. No part of this document may be publicly disclosed without the written consent of Philip Morris Products S.A.

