APPENDIX D HUMAN PUFFING TOPOGRAPHY PARAMETERS**Per-Puff Parameters**

Description	Variable	Unit
Puff number	Ni	
Puff volume	Vi	mL
Puff duration	Di	s
Average puff flow	Qmi	mL/s
Peak flow	Qci	mL/s
Inter puff interval	li	s
Sum of li and Di	DFi	s
Peak flow position	PosQci	%

Per-Product use experience Parameters

Description	Variable	Formula	Unit
Total number of puffs	NPC	$\sum Ni$	
Total puff volume	TVOL	$\sum Vi$	mL
Average puff volume	AvgVi	$\sum Vi / NPC, i=1 \dots NPC$	mL
Average puff duration	AvgDi	$\sum Di / NPC, i=1 \dots NPC$	s
Total puff duration	TDi	$\sum Di$	s
Average flow	AvgQmi	$\sum Qmi / NPC, i=1 \dots NPC$	mL/s
Average peak flow	AvgQci	$\sum Qci / NPC, i=1 \dots NPC$	mL/s
Total inter puff interval	Tli	$\sum li$	s
Average inter puff interval	Avgli	$\sum Qci / NPC, i=1 \dots NPC$	s
Total puffing duration	TDFi	$\sum DFi$	s
Puff Frequency	PFeq	$NPC/(TDFi/60)$	

Confidentiality Statement

Data and information contained in this document are considered to constitute trade secrets and confidential commercial information, and the legal protections provided to such trade secrets and confidential information are hereby claimed under the provisions of applicable law. No part of this document may be publicly disclosed without the written consent of Philip Morris Products S.A.

Signature Page for VV-TMF-00031 v2.0

Reason for signing: Approved	Name: [REDACTED] Role: A Date of signature: 19-Oct-2021 09:25:03 GMT+0000
------------------------------	---

Reason for signing: Approved	Name: [REDACTED] Role: A Date of signature: 19-Oct-2021 13:44:34 GMT+0000
------------------------------	---

Reason for signing: Approved	Name: [REDACTED] Role: A Date of signature: 19-Oct-2021 13:46:30 GMT+0000
------------------------------	---

Reason for signing: Approved	Name: [REDACTED] Role: A Date of signature: 20-Oct-2021 11:22:17 GMT+0000
------------------------------	---

Signature Page for VV-TMF-00031 v2.0

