- Changes in electrocardiogram (ECG) from baseline (heart rate, PR, QRS, QT, QTcF interval)
- Changes in vital signs from baseline (systolic and diastolic blood pressure, pulse rate and respiratory rate)
- Concomitant medication
- Changes in standard spirometry from baseline (FEV1, FEV1% predicted, FVC, FVC% predicted, FEV1/FVC)
- Changes from baseline in clinical chemistry, hematology, and urine analysis safety panel

Exploratory Objectives and Endpoints:

1. To describe the associations between P4M3 Gen 2.0 HPT parameters, PD and PK parameters.

Related Endpoints (Day 1 to Day 3):

- Score from product liking by the VAS-liking assessment and C_{max} , T_{max} , and $AUC_{0-\infty}$ PK endpoints
- Score from product liking by the VAS-liking assessment and per-product use experience parameters from the MDEDTR puffing topography device for 2 variants of P4M3 Gen 2.0

Additional Study Assessments (for eligibility assessment and baseline characteristics):

- Serology for human immunodeficiency virus (HIV) 1/2 and hepatitis B and C
- Pregnancy test (all females)
- Urine cotinine test
- Urine drug test including testing for amphetamine type substances, barbiturates, benzodiazepines, cannabinoids, cocaine, opiates
- Alcohol breath test
- Nicotine dependence assessed by Fagerström Test for Nicotine Dependence
- Cytochrome P450 2A6 (CYP2A6) activity expressed as trans-3'-hydroxycotinine / cotinine molar metabolite ratio in plasma

Study Hypothesis:

This study is exploratory in nature and there is no pre-specified hypothesis to be tested.

Philip Morris Products S.A.
 P4M3 Gen 2.0, P4-PK-04-US
 [REDACTED] Statistical Analysis Plan Number CA34617

[figure not shown]

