7.3 Inferential Analysis

An analysis of covariance (ANCOVA) will be conducted by product use. The PK parameters will be transformed in the natural logarithmic scale. The model will include terms for sequence, period and product liking by the VAS-liking assessment. The effect of VAS-liking will be analyzed in different models with VAS-liking at T_1 (after 4 minutes), T_2 (after 10 minutes), and T_3 (after 15 minutes). The results of this analysis will be presented by product in terms of:

- The percentage of variance explained by product liking by the VAS-liking assessment.
- The standardized effect of product liking by the VAS-liking assessment on the endpoint, defined as the mean effect divided by the square root of its variance.

The ANCOVA analysis will be performed using the following SAS code:

```
PROC MIXED data=<> method=type3;  
By product;  
class subject sequence period;  
model log(PK parameter) = sequence period liking_score/ddfm=KR solution;  
run;
```

Another analysis of covariance (ANCOVA) will be conducted similarly to the above with the exception that it will be performed overall using mixed effects ANCOVA where the model will include, in addition, the subject as a categorical random effect to model the within subject correlations.

The same model will also be used to perform the analysis for human puffing topography parameters (total number of puffs, total puff volume, and total puff duration) to estimate the effect of VAS-liking score on the topography parameters.

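### Liking is to be related to the per-product puffing parameters, but the SAP models only three of 11 and does not declare the cut, so average puff duration, average puff volume and both flow parameters get no estimate

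*Protocol*

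**What the plan says.** - **Endpoint.** Protocol section 3.3 pairs liking with the topography parameters: "Product liking by the VAS-liking assessment and per-product use experience parameters from the MDEDR puffing topography device". SAP section 2 carries the same pairing: "Score from product liking by the VAS-liking assessment and per-product use experience parameters". Neither restricts the list. The PK item beside it in both documents does: it names C_max, T_max and AUC_0-infinity.
- **Link to the analysis.** Protocol section 12.7 refers back to section 3.3 for its endpoints ("Exploratory analyses endpoints are listed in section" 3.3). Section 12.7.2 asks for "The standardized effect of product liking by the VAS-liking assessment on the endpoint", together with the percentage of variance explained.
- **Parameter list.** The table in Protocol Appendix D headed "Per-Product use experience Parameters" has 11 rows. SAP Table 8.2 has the same 11.
- **What is modelled.** SAP section 7.3 applies the liking model to "human puffing topography parameters (total number of puffs, total puff volume, and total puff duration"). The programmer note under the shell for Tables 15.2.2.2.4 to 15.2.2.2.7 names the same three.
- **Declared changes.** SAP section 11 lists two: the randomized population is dropped, and a CA35 versus CM35 comparison is added. The choice of three topography parameters is not mentioned.

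**The concern.** The exploratory objective is to describe how liking relates to the way the product is puffed. Protocol section 2.1.2 says that users differ notably in topography, "especially puff duration, puff frequency, and flow rate", and adds that experienced users may draw more nicotine with slower, longer puffs. Yet no flow parameter and no per-puff average enters a liking model.

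The three modelled outcomes are all totals, and each is built on puff count. A link between liking and longer or slower individual puffs would reach them mixed with variation in how many puffs were taken. The planned tables could then show a weak association where the per-puff parameter would show a clearer one. The titles of Tables 15.2.2.2.6 and 15.2.2.2.7 speak of per-product parameters in general, so a reader of the report would not see that most were left out.

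**Working it through.** The plan states no figure for this point, so the check is a count, a set of identities and one illustration.

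**1. Count** (Appendix D and SAP Table 8.2 against SAP section 7.3)

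- Listed: puff number (NPC), total volume (TVOL), average volume, average duration, total duration (TDi), average flow, average peak flow, total inter-puff interval, average inter-puff interval, total puffing duration (TDFi), puff frequency = 11.
- Modelled: NPC, TVOL, TDi = 3.
- Not modelled: 11 − 3 = 8.

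**2. Which of the eight add something**

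The use period is 6 minutes ± 30 seconds, that is 5.5 to 6.5 minutes, or ± 0.5/6 = 8.3%. TDFi sums puffs and intervals, so for a subject who puffs through the period it is nearly constant. Then:

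- puff frequency = NPC/TDFi is close to a rescaled puff count;
- total interval = TDFi − TDi is close to a constant minus total duration;
- average interval = (TDFi − TDi)/NPC follows from the two modelled quantities, and mainly from puff count if puffs fill a small part of the period (an assumption, as the documents give no figure).

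That covers four of the eight, counting TDFi itself. The other four:

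- average duration = TDi/NPC and average volume = TVOL/NPC are ratios of modelled totals. The percentage of variance and t-value for numerator and denominator do not give those for the ratio.
- average flow enters only through TVOL = TDi × mean flow, where the mean is weighted by puff duration and so only approximates the tabulated average.
- average peak flow is not a function of the three totals.

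**3. Illustration of dilution**

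All inputs here are assumed: CVs of 40% (count), 35% (average duration) and 25% (flow), independent components, log scale, and liking linked to one component only, with correlation 0.5 (25% of variance).

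- Log SD = √ln(1 + CV²): √ln 1.16 = 0.385; √ln 1.1225 = 0.340; √ln 1.0625 = 0.246.
- SD of log total duration = √(0.385² + 0.340²) = 0.514. SD of log total volume = √(0.514² + 0.246²) = 0.570.
- Correlations among the totals: 0.385/0.514 = 0.75; 0.514/0.570 = 0.90; 0.385/0.570 = 0.68. The first principal component of that correlation matrix carries 85%.
- Liking linked to average duration: 0.5 × 0.340/0.514 = 0.33 (11%) in total duration; 0.5 × 0.340/0.570 = 0.30 (9%) in total volume; 0 in puff count.
- Liking linked to flow: 0.5 × 0.246/0.570 = 0.22 (5%) in total volume.

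Other assumptions move these figures in both directions:

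| Assumption | First component | Total duration | Total volume | Puff count |
|---|---|---|---|---|
| CVs 40/35/25%, independent | 85% | 11% | 9% | 0% |
| Same CVs, count and average duration correlated −0.5 | 76% | 4% | 3% | 6% |
| CVs 20/40/40%, independent | 68% | 20% | 11% | 0% |

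The last three columns show the variance explained when liking is linked to average duration. In row 2 the SD of log total duration is √(0.385² + 0.340² − 0.385 × 0.340) = 0.365, and r = 0.5 × (0.340 − 0.5 × 0.385)/0.365 = 0.20. In row 3, r = 0.5 × 0.385/0.433 = 0.44.

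**The case against.** The other side has real points.

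- *The choice was made openly and before the data.* The three parameters are named in SAP section 7.3, the same three appear in in-text Table 9, and the SAP is to be final before database lock. Protocol section 12.1 leaves full detail to the SAP, and section 12.7.2 names only PK parameters, reaching topography through its general reference to the endpoint. This stands against any inference of concealment. It does not close the gap between an unrestricted endpoint, repeated in the SAP itself, and a restricted analysis.
- *Some of the missing result can be recovered.* On the log scale, log average duration is log total duration minus log puff count. With complete data, its liking slope in the by-product model is therefore exactly the difference of two fitted slopes, and SAS output is a planned listing. But the difference comes without a standard error, the shell shows no slopes, and section 7.3 does not say whether topography outcomes are logged. For flow the relation is only approximate.
- *A narrow set is reasonable* with 36 subjects and liking entered at three time points. All topography parameters are still summarised and listed. That is fair as far as it goes, but summaries by product do not show an association with liking.

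A reader might also infer that no association with puff duration is estimated at all. The documents do not support that: total puff duration is one of the three outcomes, and it is average duration that is missing.

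**Conclusion.** The endpoint covers 11 parameters and the analysis three, and SAP section 11 does not record the reduction. No liking association is estimated for average puff duration, average puff volume, average flow or average peak flow.

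Two stronger readings go too far. One is that eight of 11 unmodelled parameters means that share of the information is lost; with use fixed at about 6 minutes, four of the eight largely repeat puff count and total duration, provided that subjects puff through the period. The other is that the three totals carry essentially one signal and so hide a known amount of association. The 85% and the 9 to 11% hold only under assumed CVs and independence. Two other plausible sets of assumptions gave 68% and 76% for the first component, and 4% to 20% for total duration. They show how dilution works, not how large it would be here.

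The point is minor: the study tests no hypothesis and the main PK analysis is unaffected. It is worth making because the data are already collected and the change is small.

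**What to change.** In SAP section 7.3 and the programmer note to Tables 15.2.2.2.4 to 15.2.2.2.7, run the same liking model on the remaining parameters of Table 8.2. At minimum, add average puff duration and average flow. Name in SAP section 11 any parameter left out, with the reason. Declaring the omission alone would tidy the record but would still give no estimate for the missing parameters.

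The cost is extra rows from existing code. For two variants and three liking time points, the by-product fits now number 2 × 3 × 3 = 18. They become 2 × 3 × 5 = 30 with the minimum addition, or 2 × 3 × 11 = 66 with all parameters. The overall fits go from 3 × 3 = 9 to 15 or 33. The downside is more exploratory estimates to read, so they should be reported descriptively.

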4 INVESTIGATIONAL PLAN

4.1 Overall Study Design and Plan

This is a single-center, randomized, controlled, open-label, cross-over study in healthy subjects to investigate the nicotine pharmacokinetic profiles of two variants of P4M3 Gen 2.0 an electronic nicotine delivery system (ENDS), compared to cigarettes. In addition, PD effects (subjective effects and related behavioral assessments) will be evaluated to provide further insights on product evaluation. The study will be conducted with 3 periods and in a 6 sequence-cross-over design.

A Screening Visit will be conducted within 28 days (Day -29 to Day -2) prior to Admission (Day -1) to the investigational site ([Figure 2](#)). A demonstration of P4M3 Gen 2.0, without product use, will be done by the investigational site staff during the Screening Visit. A sufficient number of subjects will be screened to ensure that 36 subjects will be randomized into the study.

Confidentiality Statement

Data and information contained in this document are considered to constitute trade secrets and confidential commercial information, and the legal protections provided to such trade secrets and confidential information are hereby claimed under the provisions of applicable law. No part of this document may be publicly disclosed without the written consent of Philip Morris Products S.A.

[figure not shown]

Figure 2 Study Design

Qualified subjects will return to the investigational site for Day -1. Subjects should have fasted for at least 10 hours prior to the safety laboratory assessments. After confirmation of eligibility, subjects will be enrolled. All subjects that are not enrolled will be considered as screen failures.

On Day -1, enrolled subjects will perform a product test using P4M3 Gen 2.0 Classic Auburn 3.5% (CA35) variant *ad libitum* for up to 10 minutes. After the product test, subjects not willing and/or not ready to use P4M3 Gen 2.0 during the study will be discontinued from the study, will enter the 3-day Safety Follow-up and will be replaced.

Confidentiality Statement

Data and information contained in this document are considered to constitute trade secrets and confidential commercial information, and the legal protections provided to such trade secrets and confidential information are hereby claimed under the provisions of applicable law. No part of this document may be publicly disclosed without the written consent of Philip Morris Products S.A.

Subjects willing and ready to use 2 variants of P4M3 Gen 2.0 during the study after product test will start their confinement period of 3 days. The brand of subjects' cigarettes will be recorded.

36 subjects will be randomized to 1 of 6 possible sequences of product use on Day 1 to Day 3 (see [Figure 2](#)).

On Day 1 to Day 3, after at least 12 hours of abstinence from any nicotine/tobacco containing products (nicotine wash-out), subjects will smoke a cigarette or use a variant of P4M3 according to randomized product use sequence *ad libitum* for 6 minutes (\pm 30 seconds). The weight of each P4M3 Gen 2.0 Cartridge will be determined before and after product use to estimate the amount of nicotine delivered in the aerosol during the 6 minutes *ad libitum* use period. Subjects will use a variant of P4M3 Gen 2.0 with the MDEDR puffing topography device connected with data recording *ad libitum* for 6 minutes (\pm 30 seconds).

Subjects will complete questionnaires about product evaluation, craving and liking assessments.

The start of product use of the 6 minutes *ad libitum* use period will be defined as T_0 . T_0 on Day 1 to Day 3 should be at approximately the same time in the morning, within a window of \pm 20 minutes. Venous blood samples will be obtained according to the standard operating procedures (SOPs) at the investigational site.

On Day 1, 15 blood samples will be collected for determination of nicotine concentration at the following time points in relation to T_0 with a time window as indicated in brackets:

Prior to T_0 :

- $T-1$: 5 minutes (\pm 1 minute)

After T_0 :

- $T1$ after 1 minute (+ 30 seconds)
- $T2$ after 2 minutes (+ 1 minute)
- $T3$ after 4 minutes (+ 1 minute)
- $T4$ after 6 minutes (+ 1 minute)
- $T5$ after 8 minutes (+ 1 minute)
- $T6$ after 10 minutes (+ 1 minute)
- $T7$ after 12 minutes (+ 1 minute)
- $T8$ after 15 minutes (\pm 2 minutes)
- $T9$ after 30 minutes (\pm 2 minutes)

Confidentiality Statement

Data and information contained in this document are considered to constitute trade secrets and confidential commercial information, and the legal protections provided to such trade secrets and confidential information are hereby claimed under the provisions of applicable law. No part of this document may be publicly disclosed without the written consent of Philip Morris Products S.A.

- T10 after 1 hour (\pm 5 minutes)
- T11 after 2 hours (\pm 5 minutes)
- T12 after 4 hours (\pm 5 minutes)
- T13 after 10 hours (\pm 5 minutes)
- T14 after 24 hours (\pm 10 minutes) (Day 1 and Day 2 only)

On Day 2, 14 blood samples will be collected for determination of nicotine PK after allocated product use at the same time points, except timepoint T-1. The sample T14 after T_0 on Day 1 will also be used to determine the nicotine baseline concentration prior to T_0 on Day 2 and similarly, T14 after T_0 on Day 2 for nicotine baseline concentration prior to T_0 on Day 3.

On Day 3, 13 blood samples will be collected for determination of nicotine PK after allocated product use. The sample T14 after T_0 on Day 3 will not be collected.

On Day 1 to Day 3, subjective effects of liking and craving will be assessed using a VAS (100 mm going from “strong disliking” to “strong liking” for VAS liking, and from “no craving” to “strong craving” for VAS craving) at the following time points in relation to T_0 :

Prior to T_0 (for VAS craving assessment only)

- T-15: within 15 minutes prior to T_0 with a time window as indicated in brackets

After T_0 : (for VAS craving and VAS liking assessment)

- T1 after 4 minutes (\pm 1 minute)
- T2 after 10 minutes (\pm 1 minute)
- T3 after 15 minutes (\pm 1 minute)
- T4 after 30 minutes (\pm 2 minutes)
- T5 after 1 hour (\pm 5 minutes)
- T6 after 2 hours (\pm 5 minutes)
- T7 after 4 hours (\pm 5 minutes)
- T8 after 10 hours (\pm 5 minutes)

Additional subjective effects will be assessed on Day 1 to Day 3 by the ABOUT-Product experience questionnaire administered within 1 to 2 hours after T_0 .

On Day 2 and 3, additional blood samples will be taken for determination of the nicotine concentration to evaluate terminal elimination half-life ($t_{1/2z}$) in relation to T_0 from Day 2 at the following time points with a time window as indicated in brackets:

Confidentiality Statement

Data and information contained in this document are considered to constitute trade secrets and confidential commercial information, and the legal protections provided to such trade secrets and confidential information are hereby claimed under the provisions of applicable law. No part of this document may be publicly disclosed without the written consent of Philip Morris Products S.A.

- T1z after 8 hours (\pm 5 minutes) after T₀ from Day 2
- T2z after 12 hours (\pm 5 minutes) after T₀ from Day 2,
- T3z after 16 hours (\pm 10 minutes) after T₀ from Day 2,
- T4z after 20 hours (\pm 10 minutes) after T₀ from Day 2

After enrollment at Admission, the use of any other tobacco and nicotine containing products different from the product assigned for 6 minutes *ad libitum* use on Day 1 to Day 3, will not be allowed. Use of tobacco and nicotine containing products will not be restricted after the subject has been discharged from the investigational site on Day 3.

After discharge at Day 3, the subjects will enter a 3-day Safety Follow-Up Period (FU Period) during which AE/SAEs reported by the subjects will be collected and the follow-up of AEs/SAEs ongoing at discharge will be conducted by the investigational site (section 8.2.6).

Subjects who will be discontinued from the study before enrolment will be replaced. After enrollment but before randomization, subjects who will be discontinued from the study will enter the 3-day Safety Follow-Up Period and will be replaced. However, subjects that are discontinued after randomization will not be replaced.

